11.4.4 BlueWind RENOVA iStim™ System Treatment

Treatment will include a daily stimulation of a minimum of 30 minutes and a maximum of 2 hours, per physician discretion.

Subject therapy parameters (frequency, pulse width and current) will be adjusted according to the individual patient sensations and according to the above specified range. Treatment parameters set at each visit will be recorded in the CRF.

11.4.5 BlueWind RENOVA iStim™ System Follow Up Visits – Visits 4-8

Patients will attend the clinic at 1-, 3-, 6-, 9- and 12-months post system activation. Patients will be asked to fill in an electronic voiding diary (a 3-day diary at the 1-, 3- and 9-months post activation visits and a 7-day diary at the 6- and 12-months visits), immediately prior to every follow-up visit. Only after electronic diary information is entered to the EDC the tentatively scheduled visit will be confirmed.

Patients may receive several treatment programs to choose from based on treatment effect and comfort and accordingly may be asked to fill a voiding diary after each change.

During these visits, patients will be asked about their urinary symptoms, discomforts that might have been felt or other physiological or technical problems that might have arisen. Physical examination will be performed and patients will be asked to submit a sample of urine for urinalysis at each follow-up visit. If the urinalysis or the patient's symptoms suggest urinary tract infection, urine sample will be sent for culture and sensitivity. If culture results suggest urine tract infection, follow-up visit will be re-scheduled for after treatment.

Adverse events will be recorded in the patient's CRF, according to specific categories, as defined in section 18 of the protocol.

The device will be inspected, stimulation parameters setting will be re-evaluated and system performance parameters and usage information will be recorded in the CRF. Any change in OAB related medications or dosage will be recorded in the patient's CRF. During the 6- and 12- months follow-up visits quality of life (OAB-q) PGI-I and BSW questionnaires will be collected, as well as information on existence of mixed fecal and urine incontinence and severity of the fecal incontinence will be collected.

Sensory and motor thresholds will be assessed and recorded during each follow-up visit and leg circumference will be measured and recorded.

Specific activities and questionnaires associated with each follow-up visit is outlined on section 24; Study Schedule.

At the last visit, 12 months post activation, optimal treatment parameters and treatment regimen will be determined and adjusted on the device.

Number	Revision / Date	Page
G02-CLP-0002_US	Rev. 08 / 27 July 2021	45 of 75

11.4.6 BlueWind RENOVA iStim™ System Long-Term Follow Up (LTF) Visits – Visits 9-12

Long term follow-up visits will be performed at 18, 24, 30, 36-months post activation.

If a subject already completed the 12-months follow-up and exited the study, she will be invited for a Long-Term Follow-Up Consent Visit in which, following her consent to participate in the long-term follow-up study, some eligibility criteria will be verified and treatment parameters setting will be performed. Subjects will enter the visit schedule using their original system activation date. Any visit that has already passed will not be counted as a missed visit.

If the subject discontinued treating herself when she exited the study and is activated again she will be asked to treat herself for 30 minutes, twice a day, for at least 4 weeks prior to completing the first LTF visit. During this period, she will be asked to complete a modified daily diary to capture incontinence episodes, time to treatment effect, and symptom improvement questions.

Subjects continuing to the long-term follow-up will be asked to treat themselves per physician discretion but not less than two 30-minute treatment per week.

All follow-up visits will require completion of 3-day voiding diary by the patient before coming to visit.

Follow-up visits 10 (24-months) and 12 (36-months) will be performed in clinic and will be similar to the 6 and 12-months follow-up visits

Follow-up visits 9 and 11 will be performed over a phone call unless the treatment is not effective enough or treatment parameters are not optimal or patient is experiencing an AE or device malfunction. In such cases the patient will arrive to the clinic and a visit similar to the 1, 3, and 9- months post activation will be performed.

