10.3.3 Other Endpoints

The following endpoints will be assessed as other endpoints for the 6-, 12-, 24- and 36-months post activation, without formal hypothesis testing and type I error control.

- Incidence of procedure or device related adverse events from 12- to 36-months post activation
- Patient Global Impression of Improvement (PGI-I) score
- Treatment Benefit, Satisfaction, and Willingness to Continue (BSW)
- Reduction in the average number of severe/large urgency related incontinence episodes
- Improvement in OAB-q (HRQL and symptoms severity).
- Changes in the following OAB symptoms as measured by voiding diary compared to baseline:
 - Reduction in the number of micturition episodes.
 - o Reduction in the number of urgency related incontinence episodes.
 - Reduction in degree of urgency prior to void on Patient Perception of Intensity of Urgency Scale (PPIUS) from 0-4.
 - Reduction in severity of incontinence episodes (amount leaked).
- Proportion of dry subjects following treatment with the RENOVA iStim System as measured by 3
 consecutive days of a patient voiding diary
- Assessment of fecal incontinence symptoms in patients suffering from mixed fecal and urine incontinence
- Patient compliance with treatment
- Duration from treatment initiation to symptoms improvement (in subset of patients who stopped treatment after completing the 12-month visit and started again when consented for the long-term follow-up).
- Device usage

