Subjects who already completed the 12-month follow-up visit and exited the study prior to the addition of the long-term study visits will be invited for a consent visit in which, following her consent to participate, some eligibility criteria will be verified. Screening will include the following:

- New medical and surgical history review since the 12-month visit
- Medication use review (listing of type and doses)
- Physical and neurological examination and urinalysis will be performed. If the urinalysis suggests urinary tract infection, urine sample will be sent for culture and sensitivity.
- Urine or blood pregnancy test (if bearing potential).
- Subjects will receive a 3-day consecutive voiding diary and will be instructed to begin completing the
 diary immediately after the visit to record, among other things, instances of urgency urinary
 incontinence, number of voids per day, degree of urgency prior to voiding/leaking, severity of leaking
 episodes and number of stress related incontinence episodes per day.
 - If the subject discontinued treating herself after completion of the 12-month visit, she will be asked to complete a modified daily diary to capture incontinence episodes, time to treatment effect, and symptom improvement questions.
- Subjects will undergo parameters' setting, and will be re-trained for system home use. Device activation, as well as parameter setting will be performed using the Clinician Programmer according to the BlueWind Clinician Manual.

Number	Revision / Date	Page
G02-CLP-0002_US	Rev. 08 / 27 July 2021	42 of 75

11.4.2 BlueWind RENOVA iStim™ Implantation – Visit 2

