This endpoint is defined only for patients with baseline number of voids per day of at least 8 and baseline number of urgent episodes (PPIUS 3 or 4) of at least 9 per 7-day diary. It is expected that 70% of enrolled subjects will meet these criteria.

Sample size requirements to evaluate this secondary endpoint are calculated in the same manner as the primary, under the following assumptions:

- Significance level = 0.025 (one-sided)
- Power ≥ 85%
- Assumed treatment success rate at 6 months = 61%
- Prespecified performance goal = 45%

A total of 89 evaluable subjects are required. Assuming 15% attrition rate, a total of 105 subjects meeting the criteria described above is needed. With 70% of enrolled subjects meeting the analysis criteria, 150 total sample size is sufficient to evaluate the secondary endpoint.

The total sample size for the OASIS trial is 150 subjects.

10 Data Derivation and Transformation

Data not specifically recorded on a CRF will be derived as follows:

- Study Duration [days] = Date of Last Visit Date of First Visit + 1.
- HbA1c values will be reported in units of mmol/mol. For cases of HbA1c reported in percentage, the following conversion formula will be used:

Document ID	Revision / Date	Page
G02-CLP-0009	Rev. 06 / 18 May 2022	16 of 26

HbA1c (mmol/mol) = $[HbA1c (\%) - 2.15] \times 10.929^{1}$

- Coding of Adverse Events will be done using the most recent MedDRA version.
- Coding of Concomitant Medication will be done using the most recent WHO Drug dictionary version.
- Baseline will be defined as the value at the "Enrollment and Screening" visit unless noted otherwise.
- OAB duration at baseline from Date of OAB Diagnosis [years] = Date of Screening Date of OAB Diagnosis/365.25.
- Partial dates that are required for analysis will be imputed in the following fashion:
 - o Dates with missing month and day will be imputed as July 1st.
 - o Dates with missing day only will be imputed as the 15th of the month.
- Since querying of paper diaries is not possible at the time of completion and not feasible in an accurate
 manner afterwards, no query management process is used for the paper diaries. In its place a set of
 automatic rules will be applied to correct discrepancies in the paper diaries, as detailed in the appendix
 to the SAP.

11 Interim Analysis

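### Restart endpoint: no off-treatment diary is required and no reference or onset rule is defined, so residual benefit cannot be separated from re-response and can be recorded as rapid onset

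*Protocol*

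**What the plan says.** **The endpoint.** Protocol 10.3.3 lists "Duration from treatment initiation to symptoms improvement (in subset of patients who stopped treatment after completing the 12-month visit" and restarted on joining the long-term follow-up. The Synopsis and 13.5.6 repeat it. It is one of the other endpoints, with no formal test and no type I error control.

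**The restart.** Protocol 11.4.1 describes the consent visit for women who had already left the study: "Subjects will undergo parameters' setting, and will be re-trained for system home use". Device activation is listed at the same visit. Under 11.4.6, a woman who had stopped then treats "for at least 4 weeks prior to completing the first LTF visit".

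**The diaries.** Two are named.
- The modified daily diary is tied by 11.4.6 to the resumed-treatment weeks: "During this period, she will be asked to complete a modified daily diary to capture incontinence episodes, time to treatment effect, and symptom improvement questions". The Synopsis agrees.
- The 3-day diary comes from the consent visit in 11.4.1: "Subjects will receive a 3-day consecutive voiding diary and will be instructed to begin completing the" diary straight after that visit. The schedule in Section 26 marks both diaries at the consent visit.

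**The reference value.** SAP Section 10: "Baseline will be defined as the value at the 'Enrollment and Screening' visit unless noted otherwise". No restart baseline is noted in either document. The endpoint lists in SAP 8.4 and 12.6.3 omit this endpoint. SAP Section 13 provides only descriptive summaries for the long-term phase.

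**The concern.** A time to improvement after restart needs to know how the woman was just before she restarted. The plan does not secure that record. The daily diary runs on treatment, and the 3-day diary may or may not overlap the first sessions. The one reference that certainly exists is the screening diary, which predates implantation and is more than a year old by the time of restart.

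A woman who keeps part of her first-year benefit while off treatment may already be well below her screening leak rate on the first day of restart. If screening is the reference, she is recorded as improving almost at once, whatever the restarted stimulation does. If the first days of the restart diary are the reference, they may already contain an early response, which would then be missed. Neither separates what was left over from what came back.

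The gap also cannot be repaired later. An off-treatment level that was not recorded before treatment resumed cannot be recovered at analysis, so defining the endpoint in the SAP is not enough by itself.

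**Working it through.** The documents give no sample size, expected value or analysis rule for this endpoint, so there is no figure to reproduce. The check has two parts.

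**1. The order of events**

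| Step | Source | Is the off-treatment state recorded? |
|---|---|---|
| 7-day screening diary | Protocol 11.4.1 | Before implantation only |
| Exit after month 12; woman stops treating | Protocol 11.4.6 | No diary specified |
| Consent visit: parameters set, device activated, re-training | Protocol 11.4.1 | No symptom diary completed before activation |
| 3-day diary, begun after that visit | Protocol 11.4.1, Section 26 | Not settled: the first home session is not dated relative to it |
| Modified daily diary, about 4 weeks | Protocol 11.4.6, Section 26 | No: runs during resumed treatment |

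An off-treatment level therefore exists only if a woman happens to finish the 3-day diary before her first session. Nothing requires this, and sites may differ.

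**2. How large the effect could be (illustration only)**

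Assumptions that are not in the documents:
- daily leaks are Poisson;
- improvement means a leak count over the first 3 diary days of at most 50% of the reference;
- restarting has no effect at all;
- the woman keeps a fraction r of reduction while off treatment;
- the reference rate b is known without error.

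The lowest b comes from the eligibility floor in Protocol 10.7.1: 9 leaks in 7 days, 9/7 = 1.29 per day. The values 3 and 4.8 per day are assumed.

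Against screening, P(improved) = P(X ≤ k), where X is Poisson with mean 3b(1 − r) and k is the whole part of 0.5 × 3b.

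Worked case: b = 4.8 gives 0.5 × 14.4 = 7.2, so k = 7. With r = 0.30 the mean is 14.4 × 0.70 = 10.08, and P(X ≤ 7) = 0.21.

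| b per day | k | r = 0 | r = 0.30 | r = 0.40 | r = 0.50 |
|---|---|---|---|---|---|
| 1.29 | 1 | 10% | 25% | 33% | 43% |
| 3.0 | 4 | 5.5% | 25% | 37% | 53% |
| 4.8 | 7 | 2.5% | 21% | 37% | 57% |

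The r = 0 column is chance alone.

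Against the woman's own off-treatment rate b(1 − r), k becomes the whole part of 0.5 × 3b(1 − r). At r = 0.50 the cut-offs are 0, 2 and 3, and the chances fall to 15%, 17% and 7% for b = 1.29, 3.0 and 4.8. At 1.29 per day with r = 0.30 or 0.40 the cut-off stays at 1, so changing the reference changes nothing there. The gain is smallest in women with few leaks.

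**The case against.** Three stronger readings are tempting, and the documents do not support them.

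**That residual benefit is in fact counted as fast onset.** This would need a rule comparing leaks after restart with the screening diary, and there is none. The endpoint bullet does not mention baseline, unlike the neighbouring bullet on diary symptoms. The SAP default gives way where something else is noted. The daily diary also carries questions on time to effect and symptom improvement, so onset might be self-reported rather than a leak threshold. If the reference were her state at restart, residual benefit would not count as onset. This stands: what is shown is a missing definition that leaves the bias open, not a bias that has occurred.

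**That no diary covers the off-treatment state.** The order of the 3-day diary and the first session is unstated. Activation at the same visit makes overlap plausible, but does not establish it.

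**That this is the trial's only information on onset.** All implanted women are scheduled for diaries at 1 and 3 months after first activation, and SAP 6.1.2 defines a one-month responder set against the untreated baseline. The restart endpoint is the only one framed as a time to improvement, in a subset.

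The restart was also not designed as a withdrawal-and-rechallenge test. No washout is set, reasons for stopping are not given, and the women are self-selected and unblinded. One more diary would not make it causal evidence. Finally, the percentages rest on assumed inputs, and the 57% comes from assuming a true 50% reduction and then testing for 50%.

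What survives is that no off-treatment record is required, and that neither screening nor the first restart days can stand in for it.

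**Conclusion.** The point holds in limited form. For women who stopped after month 12 and restart, no off-treatment diary is guaranteed, no reference or onset rule is defined, and the SAP does not list the endpoint. Residual benefit can be recorded as rapid onset and cannot be separated from re-response.

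Under the stated assumptions, 30% to 50% residual benefit gives about 21% to 57% apparent improvement in 3 days with no restart effect, against about 2.5% to 10% with no residual benefit. These figures show that the problem could be material. They do not estimate what happened, because the leak rates above the eligibility floor, the residual benefit, the Poisson model and the 50% rule are all assumed, and the size of the subset is unknown.

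The consequence is confined to a descriptive endpoint in a subset. This is a cheap improvement, not a threat to the trial's conclusions.

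**What to change.** **Protocol 11.4.1, 11.4.6 and Section 26.** For women who had stopped treating, sequence the 3-day diary already issued at the consent visit so that it records the off-treatment state before the first resumed session, where the investigator finds this acceptable. Record the date of that first session, and begin the modified daily diary with it. When treatment resumes is for the sponsor and investigator to settle and to reconcile across these sections. The statistical requirement is only that the record exists and that its timing is known.

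**SAP 8.4, 12.6.3 and 13.** Add the endpoint. Define time to improvement from the first resumed session, with the off-treatment diary as the reference, and state the onset rule. Report how many women already met the threshold against screening before restarting. Where no off-treatment diary exists, report those women separately and describe their times as not separating residual benefit from re-response.

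**Cost.** No new visit or instrument; one extra date on the CRF. The downside is a restart up to about three days later in women who are already off treatment. A 3-day reference is also noisy, most of all in women with few leaks, so the results should stay descriptive.

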11.4.7 Unscheduled Visit

An unscheduled visit will be any visit to the clinical site other than the visits specified in the protocol. Unscheduled follow-up visits will be allowed as needed to adjust stimulation settings to optimize therapy. The Investigator or trained and qualified investigational staff will perform all procedures necessary to evaluate the study participant at these visits, and record the visit in the patient's CRFs. The investigational site Principal Investigator must be notified by the patient immediately of any unscheduled visits to any medical facility during the study period.

At certain circumstances (e.g. UTI) the subject will be requested to attend an additional visit, after the circumstance has been resolved. The relevant data will be collected again during this additional visit and used for analysis. This additional visit will be considered the formal visit for which the data will be used to evaluate study endpoint. At such circumstances the additional visit will be allowed to occur out of the window range.

Number	Revision / Date	Page
G02-CLP-0002_US	Rev. 08 / 27 July 2021	46 of 75

12. Monitoring Procedures

12.1 Monitoring Procedures and Responsibilities

Monitoring visits will be conducted at the start, during, and at the closure of the clinical study in accordance with study Monitoring Plan and in compliance with recognized Good Clinical Practices, FDA's IDE guidance document, as outlined in 21CFR§812.43(d) and 21CFR§812.46 and ISO 14155:2011 and per company's (or company designee) standard operating procedure. The Monitoring Plan will be included in a separate document and maintained by the study manager or designee. The Monitoring Plan will include detailed descriptions for each type of visit to be made during the study, including pre-study visits, site initiation visits, interim monitoring visits and close-out visits.

It is the responsibility of the study sponsor to ensure that proper monitoring of the investigation is conducted. This includes ensuring subject and investigator compliance to the protocol and study agreements, adherence to regulations, and accuracy of study data.

The clinical monitor, as a representative of the sponsor, has the obligation to follow the study closely. In doing so, the monitor will visit the principal investigator and/or sub-investigator(s) and study center at periodic intervals, in addition to maintaining necessary telephone and letter contact. The monitor will maintain current personal knowledge of the study through observation, review of study records and source documentation, and discussion of the conduct of the study with the principal investigator and staff.

All aspects of the study will be carefully monitored for compliance with applicable government regulations, with respect to current ISO 14155:2011 and Declaration of Helsinki regulations, and current SOPs.

The following factors will be taken into account when determining the frequency of monitoring visits at each center: implantation rate, total number of subjects enrolled, study phase (e.g., screening, treatment, long-term follow-up), center compliance, and monitoring findings from previous visits. The frequency of interim monitoring visits will be documented in the monitoring plan and approval from sponsor prior to each interim monitoring visit is required.

13. Statistical Considerations

This section describes the statistical methods that will be applied to the study's main endpoints. A detailed statistical analysis plan (SAP) will be written and finalized prior to trial initiation.

13.1 Introduction

This is a prospective, single arm, multi-center, open label study whose primary objective is to assess the safety and efficacy of the BlueWind RENOVA iStim™ system for the treatment of UUI. The trial's secondary objectives are to evaluate device performance, durability of effect and patient reported outcomes (PROs) such as quality of life (QoL).

The trial will be conducted in up to 30 centers.

Number	Revision / Date	Page
G02-CLP-0002_US	Rev. 08 / 27 July 2021	47 of 75

13.2 Analysis Sets

13.2.1 Safety and Efficacy Analysis Population – Intent To Treat (ITT)

The safety and effectiveness endpoints will be evaluated under principles of Intent to Treat (ITT). The analysis set will consist of all subjects for whom the implantation of the BlueWind RENOVA iStim™ system was attempted. Specifically, the analysis set will consist of all subjects for whom skin incision time was not missing.

Treatment of missing values:

- Subjects missing data "not in random" will be imputed "failure" on dichotomous endpoints
- "Failures" (not MAR) include:
 - Subject leaves the study due to related AE
 - Device explant
 - Lack of effect that results in significant increase of UUI medication
 - O Need for other 3rd line therapies for the management of UUI
- Baseline values will not be imputed
- Missing values in ITT not due to "failure" will be imputed using multiple imputation (MI).

Because MI assumes missing at random (MAR), sensitivity analyses will, as described below, be conducted to test the effects of other patterns of missingness. See Section 13.3 below for further discussing of how missing data will be handled in the efficacy analysis.

